#### 13.2 Data Review and Clarifications

The eCRF data will be reviewed against the subject's source data by the study monitors to ensure completeness and accuracy. After monitoring has occurred at the clinical sites and the eCRFs have been submitted, additional data clarifications and/or additions may be needed. Data clarifications and/or additions are documented and are part of each subject's eCRFs.

## 13.3 Regulatory Documentation and Records Retention

The Investigator is required to maintain up-to-date, complete regulatory documentation as indicated by the Sponsor and the Investigator's files will be reviewed as part of the ongoing study monitoring. Financial information is not subject to regulatory inspection and should be kept separately.

Additionally, the Investigator must keep study records and source documents until the Sponsor provides written approval for their destruction. If the Investigator retires, relocates, or for any other reason withdraws from responsibility of keeping the study records, the Sponsor must be notified and suitable arrangements made for retention of study records and source documents needed to comply with national and international regulations (generally 2 years after discontinuing clinical development or after the **latest** marketing approval).

Short Title:

**Statistical Analysis Plan
CLK027-P001**

Full Title:

**Statistical Analysis Plan
CLK027-P001 / NCT03118934**

Protocol Title: Assessing Fitting Guides in Alcon Multifocal Contact Lenses

Project Number: CLK027-P001

Reference Number:

Protocol TDOC Number: TDOC-0053461

Author:

[REDACTED]

[REDACTED]

Template Version: Version 4.0, approved 16MAR2015

Approvals: See last page for electronic approvals.

Job Notes:

This is the first revision (Version 2.0) Statistical Analysis Plan for this study. This version of the Statistical Analysis Plan is based on Version 1.0 of the study protocol.

Executive Summary:

Key Objectives:

To demonstrate noninferiority of the alternative fitting guide compared to the current fitting guide as determined by the mean number of trial lenses needed to fit each eye at the Screening/Fitting visit for all Alcon multifocal (MF) lenses combined

Decision Criteria for Study Success:

Success of this study will be based on demonstration of noninferior mean number of trial lenses needed to fit each eye of the alternative fitting guide compared to the current fitting guide, at Screening/Fitting visit for all Alcon MF lenses combined.

Table of Contents

Statistical Analysis Plan CLK027-P001 1

Table of Contents 3

List of Tables 4

List of Figures 4

1 Study Objectives and Design 5

1.1 Study Objectives 5

1.2 Study Description 6

1.3 Randomization 7

1.4 Masking 8

1.5 Interim Analysis 8

2 Analysis Sets 8

2.1 Safety Analysis Set 8

2.2 Full Analysis Set 8

2.3 Per Protocol Analysis Set 8

3 Subject Characteristics and Study Conduct Summaries 9

4 Effectiveness Analysis Strategy 9

4.1 Effectiveness Endpoints 10

4.2 Effectiveness Hypotheses 11

4.2.1 Hypothesis for the Primary Endpoint 11

█ 11

4.3 Statistical Methods for Effectiveness Analyses 11

4.3.1 Primary Effectiveness Analyses 11

█ 12

4.4 Multiplicity Strategy 15

█ 15

4.6 Interim Analysis for Effectiveness 15

5 Safety Analysis Strategy 15

5.1 Safety Endpoints 15

5.2 Safety Hypotheses 15

5.3 Statistical Methods for Safety Analyses 15

1.1 Study Objectives

PRIMARY OBJECTIVE

To demonstrate noninferiority of the alternative fitting guide compared to the current fitting guide as determined by the mean number of trial lenses needed to fit each eye at the Screening/Fitting visit for all Alcon MF lenses combined

1.2 Study Description

This is a multicenter, subject-masked, randomized, parallel, stratified, active-controlled evaluation to compare the fitting success (determined by the mean number of trial lenses needed to successfully fit each eye) using the current MF fitting guide compared to the alternative MF fitting guide for all three of the Alcon MF contact lenses (AIR OPTIX AQUA[®] Multifocal [AOA MF], DAILIES[®] AquaComfort Plus[®] Multifocal [DACP MF], and DAILIES TOTAL1[®] Multifocal [DT1 MF]).

[figure not shown]
Approximately 180 subjects will be enrolled at approximately 20 sites. To participate in the study, subjects must be current soft contact lens wearers needing presbyopia-correction, with a near spectacle ADD of +0.50 D to +2.50 D (inclusive). Each site will enroll approximately 9 subjects (6 will be monthly/weekly habitual lens wearers and 3 will be daily disposable habitual lens wearers).

Randomization for this study will be implemented in 2 parts. First, each site will be randomized to one fitting guide and will fit all subjects at their site using the assigned fitting guide (current or alternative). The purpose of this strategy is to reduce the likelihood that errors will be made in fitting the trial lenses if trying to use two similar fitting guides. Randomization of the fitting guide will be stratified by region.

Secondly, subjects who currently wear monthly/weekly contact lenses will be randomized to either AOA MF or DACP MF contact lenses (1:1 randomization). Subjects who currently wear daily disposable contact lenses will be fitted with DT1 MF contact lenses.

The expected duration of subject participation in the study is 10 ± 3 days (7 days minimum) and up to 33 days (maximum) for all subjects with a minimum of 2 scheduled visits, up to 5 scheduled visits, depending on necessity of refit dispensing and follow-up visits. The study design is presented in Figure 1-1.

Figure 1-1 Study Design

1.3 Randomization

A member of the Randomization Programming group at Alcon who is not part of the study team will generate the randomized allocation schedules applicable for the study. Each site will receive an envelope, based upon the randomization list, containing a card with the

respective fitting guide to use. Subsequently, randomization for habitual weekly/monthly lens wearers will be implemented.

1.4 Masking

This study is subject-masked. Subjects are masked only to the MF fitting guides.

1.5 Interim Analysis

Not applicable.

2 Analysis Sets

2.1 Safety Analysis Set

Safety analyses will be conducted using the safety analysis set on a treatment-emergent basis. As such, the safety analysis set will include all subjects/eyes exposed to study lenses evaluated in this study, except for the trial lenses used for parametrization and fitting at Visit 1. For treatment-emergent safety analyses, subjects/eyes will be categorized under the actual study lenses exposed.

Subjects who are lost to follow-up and their exposure to dispensed study lenses is unknown will be included in the safety data set. The dispense date for these subjects will be assumed as the first exposure date (Visit 2 Dispense 1).

2.2 Full Analysis Set

The Full Analysis Set (FAS) will include:

1. all randomized subjects to AOA MF or DACP MF as well as subjects assigned to DT1 MF and
2. who are exposed to study lenses including those used for parametrization and fitting at Visit 1

All effectiveness analyses relevant to fitting guide will be conducted according to the randomized assignment. Effectiveness analyses based upon lens brand will be conducted according to the randomized or non-randomized assignment as applicable to the habitual lens wear.

2.3 Per Protocol Analysis Set

The Per Protocol (PP) Analysis Set will include:

1. all randomized subjects to AOA MF or DACP MF as well as subjects assigned to DT1 MF and
2. all data/subjects which have not met any of the critical deviation or non-evaluable criteria identified in the Deviations and Evaluability Plan

All effectiveness analyses relevant to fitting guide will be conducted according to the randomized assignment. Effectiveness analyses based upon lens brand will be conducted according to the randomized or non-randomized assignment as applicable to the habitual lens wear.

3 Subject Characteristics and Study Conduct Summaries

Demographic information (age, sex, ethnicity, and race) will be summarized on the safety, full and PP analysis sets. Baseline characteristics on habitual lens [REDACTED] [REDACTED] will be summarized on the full and PP analysis sets. [REDACTED].

All descriptive summary statistics will be displayed with counts and percentage for categorical data, and with n, mean, standard deviation, median, minimum, and maximum for continuous data.

4 Effectiveness Analysis Strategy

This study defines one primary endpoint, [REDACTED] [REDACTED]. All effectiveness evaluations will use the FAS as the primary analysis set. Supportive analyses of the primary [REDACTED] effectiveness endpoint will be conducted using the PP analysis set only if the number of subjects excluded from PP analysis set exceeds 5% of FAS. A summary of the planned analysis strategy is presented in Table 4-1

Summary of Inferential Analysis Strategy for Effectiveness Endpoints.

For all planned inferential analyses, alternative models/methods may be considered if convergence cannot be achieved.

[REDACTED]
[REDACTED]
[REDACTED]

[REDACTED]

[REDACTED]

2.

[REDACTED]

4.1 Effectiveness Endpoints

Primary Endpoint

The primary endpoint is the number of trial lenses needed to fit each eye at the Screening/Fitting visit (Visit 1), derived from number of on-eye lens prescriptions.

[REDACTED]

4.2 Effectiveness Hypotheses

4.2.1 Hypothesis for the Primary Endpoint

The primary hypothesis to be tested is the noninferiority of the alternative fitting guide when compared to the current fitting guide in fitting. The null and alternative hypotheses are formulated based on a pre-defined noninferiority margin of 0.5 as follows:

$$H_0: \mu_{(AFG)} - \mu_{(CFG)} \geq 0.5$$

$$H_a: \mu_{(AFG)} - \mu_{(CFG)} < 0.5$$

where $\mu_{(AFG)}$ and $\mu_{(CFG)}$ denote the mean number of trial lenses used to achieve fit in each eye using the alternative and current fitting guide, respectively, at the Screening/ Fitting visit. All Alcon MF lenses are to be included.

4.3 Statistical Methods for Effectiveness Analyses

4.3.1 Primary Effectiveness Analyses

[figure not shown]
A mixed effect repeated measures model will be utilized to test these hypotheses, including terms for fitting guide, [REDACTED]

[REDACTED] Correlation between eyes will be accounted for. Fitting guide difference (Alternative minus Current) and the corresponding one-sided 95% upper confidence limit (UCL) will be computed. Noninferiority in fitting will be declared if $UCL < 0.5$ at Visit 1. The following SAS pseudo code will be used for the analysis:

```
proc sort data = one; by subject; run;
```

```
proc mixed data = one;
```

```
class subject fitting_guide lens ADD_power region eye ;  
model y = fitting_guide lens fitting_guide*lens region ADD_power/ddfm = kr;  
repeated eye /subject=subject type=(to be determined);  
lsmeans fitting_guide/ cl diff alpha=0.10 e;  
run;
```

[figure not shown]
[figure not shown]

Table 4-1 Summary of Inferential Analysis Strategy for Effectiveness Endpoints

Endpoint	Main vs. Sensitivity Approach ^a	Statistical Method ^b	Analysis Set	Missing Data Approach
Primary				
Number of lenses needed for fit at Visit 1	M	Linear mixed model ^c	FAS (as randomized)	Observed data only
Number of lenses needed for fit at	S	Linear mixed	PPS (as	Observed

[figure not shown]
Visit 1		model ^c	randomized)	data only
^a M=Main analysis approach; S=Sensitivity analysis approach				
^b Further details on statistical models are:				

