#### 9 TREATMENTS ADMINISTERED

Upon signing the informed consent form, subjects will be considered enrolled in the study and will be assigned a number in the appropriate numerical sequence. Subject numbers will be assigned by the electronic data capture (EDC) system at each investigational site.

Randomization for this study will be implemented in 2 parts. First, each site will be randomized to one fitting guide and will fit all subjects at their site using the assigned fitting guide (current or alternative). The purpose of this strategy is to reduce the likelihood that errors will be made in fitting the trial lenses if trying to use two similar fitting guides. Randomization of the fitting guide will be stratified by region.

Secondly, subjects who currently wear monthly/weekly contact lenses will be randomized to either AOA MF or DACP MF contact lenses (1:1 randomization). Subjects who currently wear daily disposable contact lenses will be fitted with DT1 MF contact lenses.

The study lenses will be dispensed in an unmasked manner by a trained study staff member. Subjects are unmasked to the study lenses that are dispensed, but will be masked to the fitting guides used to fit each eye for all study lenses.

Throughout the study, the Investigator will be responsible for the accounting of all study materials and will ensure that the study products are not used in any unauthorized manner.

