#### 11.4.1.2 Analysis Methods

A mixed effect repeated measures model will be utilized to test these hypotheses, including terms for fitting guide,

Correlation between eyes will be accounted for in this analysis.

Fitting guide difference (Alternative minus Current) and the corresponding one-sided 95% upper confidence limit (UCL) will be computed. Noninferiority in fitting will be declared if UCL < 0.5 at Visit 1.

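### The fitting guide is randomised by site, but the primary model has no site term, so the one-sided 5% error rate is exceeded if sites differ at all within region

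*SAP*

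**What the plan says.** Protocol section 9 (Treatments Administered) sets the unit of allocation: "each site will be randomized to one fitting guide and will fit all subjects at their site". SAP 1.2 repeats this. It adds that "Approximately 180 subjects will be enrolled at approximately 20 sites" and "Each site will enroll approximately 9 subjects", and on stratification, "Randomization of the fitting guide will be stratified by region".

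SAP 4.3.1 gives the SAS code for the primary analysis. The class variables are "class subject fitting_guide lens ADD_power region eye", the fixed effects are "model y = fitting_guide lens fitting_guide*lens region ADD_power/ddfm = kr", and the covariance is "repeated eye /subject=subject type=(to be determined" (the structure is left open). Neither site nor investigator appears, and there is no random statement. The only correlation named in the text is between eyes; Protocol 11.4.1.2 reads "Correlation between eyes will be accounted for in this analysis".

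Noninferiority is declared if the one-sided 95% upper confidence limit (UCL) for alternative minus current is below 0.5. Protocol 11.6 and SAP 4.4 state that overall type I error is controlled at one-sided 0.05.

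**The concern.** This is a cluster-randomised comparison. Each site contributes to one guide only, so any site-to-site difference in how many lenses are tried goes directly into the guide difference. The planned model treats all subjects as independent once region, lens, ADD power and guide are fitted. It therefore gives the guide effect subject-level degrees of freedom (about 170), although only about 20 independent units carry that comparison.

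Some correlation within sites is plausible. Site staff fit the lenses and know the assigned guide, since only subjects are masked to it, and deciding when to try another lens is likely to involve judgement. Region does not absorb site differences within a region. Kenward-Roger cannot adjust for a variance component that is not in the model.

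One UCL decides the study, and the error favours declaring noninferiority. Protocol 5.1 says the result is to support a recommendation on one global fitting guide.

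**Working it through.** **Inputs from the documents.** About 20 sites, 9 subjects per site and 180 subjects (SAP 1.2). SD 0.6, expected difference 0.25, margin 0.5, one-sided alpha 0.05, and 80 subjects (160 eyes) per group for 83% power (SAP 7, Protocol 11.10).

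**Assumptions.** Ten sites per guide, because no allocation ratio for sites is stated. ICC from 0 to 0.20, because none is given.

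**1. The plan's own figure.** With 80 per group, SE = 0.6 × √(2/80) = 0.0949. The noncentrality is (0.5 − 0.25)/0.0949 = 2.64, and on 158 df the power is 83.6%, which matches the stated 83%. Treating 160 eyes per group as independent would give 98.1%. The plan therefore counts 80 independent subjects per group at SD 0.6, with no allowance for site.

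**2. Standard error with site correlation.** With 90 subjects per guide, the SE ignoring site is 0.6 × √(2/90) = 0.0894. The design effect is DE = 1 + (9 − 1) × ICC, and the true SE is 0.0894 × √DE.

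**3. Actual error at a true difference of 0.5.** If the model uses the smaller SE, the error is 1 − Φ(1.645/√DE). For ICC 0.05, DE = 1.40 and 1.645/1.183 = 1.390, which gives 8.2%.

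**4. Simulation check.** 20,000 trials per ICC were analysed with guide, lens, guide-by-lens and region but no site, and again by site means adjusted for region. Three regions were assumed, each subject's two eyes were represented by their mean, and ADD power was left out.

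**5. Power of a site-level test.** Noncentral t on 18 df, with noncentrality 0.25 divided by the true SE.

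| ICC | DE (9 per site) | True SE | Error, no site term (formula) | Error, no site term (simulated) | Error, site means (simulated) | Site-level power, 8 / 9 per site |
|---|---|---|---|---|---|---|
| 0 | 1.00 | 0.0894 | 5.0% | 5.1% | 5.2% | 81% / 85% |
| 0.02 | 1.16 | 0.0963 | 6.3% | 6.4% | 5.0% | 77% / 80% |
| 0.05 | 1.40 | 0.1058 | 8.2% | 8.4% | 5.2% | 70% / 73% |
| 0.10 | 1.80 | 0.1200 | 11.0% | 11.2% | 4.9% | 62% / 64% |
| 0.20 | 2.60 | 0.1442 | 15.4% | 15.8% | 5.3% | 50% / 51% |

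The 8-per-site column corresponds to the 80 per group behind the stated 83%. With 8 per site the formula error is slightly lower: 7.8%, 10.4% and 14.4% at ICC 0.05, 0.10 and 0.20.

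**6. Distance from estimate to UCL (9 per site).** Ignoring site: 1.654 × 0.0894 = 0.148. At site level on 18 df: 1.734 × 0.1058 = 0.183 at ICC 0.05, and 1.734 × 0.1200 = 0.208 at ICC 0.10. The planned UCL is then too low by about 0.04 and 0.06.

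**The case against.** **The model description is partly hidden.** The prose list of terms is redacted after the fitting guide, a table footnote is not shown, and the code is labelled as pseudo code. A site term could be named in the missing text. However, the SAP presents this code as what the analysis will use, and its class, model and repeated lines are legible. A site term elsewhere would contradict the code, which would then need correcting anyway.

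**The excess depends on an unknown ICC.** This stands. At ICC 0 the planned model holds 5%, and at 0.02 the error is only 6.3%. No visible text says how many practitioners fit at a site or what triggers another trial lens, and a written guide could narrow differences between them. The direction does not depend on the value, though: any positive ICC makes the UCL too low, and the plan gives no basis for assuming zero.

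**Other parts of the plan might compensate.** They do not. The per-protocol sensitivity analysis in SAP Table 4-1 is listed with the same method. The provision for alternative models (Protocol 11.4, SAP 4) applies only if convergence fails.

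**The correction costs power.** This also stands, and the cost is given under the fix.

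**Conclusion.** The concern holds. As specified, the primary analysis does not match the unit of randomisation, and control of type I error at one-sided 0.05 is not a property of this model unless sites are identical after covariate adjustment. For assumed ICCs of 0.02 to 0.20, false noninferiority runs from about 6% to 15%, while a site-level analysis stays at about 5%. These figures rest on 10 against 10 equal sites of 9, SD 0.6 at subject level, and assumed ICCs. The missing site term itself rests on none of them. Because this single UCL decides the trial, the model should be corrected before the result is relied on.

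**What to change.** In SAP 4.3.1:

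- Add site to the class statement and add `random site;`.
- Change the repeated statement to `repeated eye / subject=subject(site)`.
- Keep `ddfm=kr`, so that the guide effect is tested on roughly 16 to 18 df (20 sites, less the two guide means and, if there are three regions, two region terms).
- State in advance what happens if the site variance is estimated at zero, since the test would otherwise return to subject-level df. Either use the NOBOUND option or compare the roughly 20 site means, adjusted for region.
- Use the same model for the per-protocol analysis.

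Amend Protocol 11.4.1.2 to say that correlation within site is accounted for as well as correlation between eyes.

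The edit is a few words of code and one sentence, with no new data. The real cost is a wider UCL and lower power. With 9 subjects per site, power is about 73% at ICC 0.05 and 64% at 0.10. With 8 per site, the like-for-like comparison with the stated 83%, it is 70% and 62%. The power statement should be redone with a stated ICC, and holding the planned power may need more sites.

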4.4 Multiplicity Strategy

A sequential gatekeeping strategy will be implemented to control testing of multiple effectiveness endpoints. Therefore, the overall type I error will be controlled at one-sided 0.05 with the following testing order:

- Noninferiority of primary endpoint
- 

4.6 Interim Analysis for Effectiveness

Not applicable.

5 Safety Analysis Strategy

5.1 Safety Endpoints

The safety endpoints are

- Adverse events
- Biomicroscopy findings
 - Limbal hyperemia
 - Bulbar hyperemia
 - Other findings
- Device deficiencies

5.2 Safety Hypotheses

There are no formal safety hypotheses in this study. The focus of the safety analysis will be a comprehensive descriptive assessment of safety endpoints listed in Section 5.1.

5.3 Statistical Methods for Safety Analyses

The analysis set for all safety analyses is the safety analysis set as defined in Section 2.1. Safety variables will be summarized descriptively.

5.3.1 Adverse Events

The applicable definition of an Adverse Event (AE) is in the study protocol. All AEs occurring from when a subject signs informed consent to when a subject exits the study will be accounted for in the reporting.

Analysis and presentation of pre-treatment and between-treatment AEs will be separated from treatment-emergent AEs occurring during the study period. A pre-treatment AE is an event that occurs after signing informed consent but prior to exposure to study lens not used for lens parametrization and fitting at Visit 1. A between-treatment AE is an event that occurs after last exposure to dispense 1 study lens but prior to exposure to dispense 2 study lens. The period for treatment-emergent AE analysis starts from exposure to study lens dispensed at Visit 2 (Dispense 1) until the subject completes or is discontinued from the study, excluding the between-treatment period.

Descriptive summaries (counts and percentages) for ocular and nonocular treatment-emergent AEs will be presented by Medical Dictionary for Regulatory Activities (MedDRA) System Organ Class (SOC) and Preferred Terms (PT). Serious AEs will be summarized separately. Additionally, relationship to lens will be identified in all AE tables. Unit of presentation for ocular AEs will be eyes and nonocular AEs will be subjects.

Individual subject's listings will be provided for pre-treatment, between-treatment and treatment emergent AEs, where any AE leading to study discontinuation will be indicated.

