#### **Safety**

Each safety variable will be summarized descriptively. AEs will be classified as treatment-emergent, based upon treatment-specific exposure, or pre-treatment. Count and percentage will be provided by relationship to device, and separate tables will be generated for ocular and nonocular AEs. Counts and percentages in each grade category will be presented for each biomicroscopy parameter. Device deficiencies will also be tabulated. Supporting subject listings describing details of each safety variable will be provided. No inferential testing will be performed for safety analyses.

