#### 11.2 Analysis Data Sets

#### 11.2.1 Safety Analysis Set

Safety analyses will be conducted using the safety analysis set on a treatment-emergent basis. As such, the safety analysis set will include all subjects/eyes exposed to study lenses evaluated in this study, except for the trial lenses used for parameterization and fitting at Visit 1. For treatment-emergent safety analyses, subjects/eyes will be categorized under the actual study lenses exposed.

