# 11.7 Safety Analysis

The safety endpoints for this study are AEs, biomicroscopy findings, and device deficiencies.

Descriptive summaries (counts and percentages) for ocular and nonocular AEs will be presented by Medical Dictionary for Regulatory Activities Preferred Terms. In addition to an overall presentation of AEs, reports will be generated for serious AEs. AEs leading to study discontinuation will be identified. Individual subject listings will be provided, as necessary.

Document: TDOC-0053461 Version: 1.0; CURRENT; Most-Recent; Effective

Status: Effective Page 46 of 54

Individual subject listings will be provided for AEs that occur after signing informed consent but prior to exposure to study lens not used for lens parametrization and fitting at Visit 1.

Each biomicroscopy parameter will be tabulated by its grade. For each biomicroscopy parameter, counts and percentages of eyes that experience an increase of  $\geq 2$  grades from baseline to any subsequent visit will be presented. Baseline is defined as Visit 2. A supportive listing will be generated which will include all biomicroscopy data from all visits for these eyes experiencing the increase.

Two listings (prior to exposure of study lenses not used for lens parametrization and fitting at Visit 1, and treatment-emergent) of device deficiencies will be provided. Additionally, each device deficiency category will be tabulated.

No inferential testing will be done for safety analysis.

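### SAP 5.3.1 sets aside a between-treatment AE class that the visible protocol does not name, so whether an event after the last Dispense 1 wear is tabulated depends on a later refit

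*SAP*

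**What the plan says.** SAP 5.3.1 sorts adverse events into three classes. The middle one, between-treatment, is "an event that occurs after last exposure to dispense 1 study lens but prior to exposure to dispense 2 study lens". The treatment-emergent window opens with exposure to the first dispensed lens and runs "until the subject completes or is discontinued from the study, excluding the between-treatment period".

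On outputs, the same section says "Descriptive summaries (counts and percentages) for ocular and nonocular treatment-emergent AEs will be presented" by System Organ Class and Preferred Term, with relationship to lens shown, eyes as the unit for ocular events and subjects for nonocular events. It adds "Serious AEs will be summarized separately", with no stated restriction by class. All three classes get individual listings, and the section says that every event from consent to exit will be accounted for.

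The protocol synopsis, under Safety, has two classes: "AEs will be classified as treatment-emergent, based upon treatment-specific exposure, or pre-treatment". Protocol 11.7 says "Descriptive summaries (counts and percentages) for ocular and nonocular AEs will be presented" by Preferred Term, and adds an overall presentation and reports of serious events. The class it singles out for a separate listing is the one before dispensed-lens wear: "Individual subject listings will be provided for AEs that occur after signing informed consent but prior to exposure to study lens" (trial-fit lenses at Visit 1 do not count as exposure). Protocol 11.2.1 and SAP 2.1 both say that "subjects/eyes will be categorized under the actual study lenses exposed".

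**The concern.** The between-treatment interval begins after the subject has already worn a dispensed study lens. Events that appear soon after lens removal are among those a reader of a contact lens safety table would expect to see counted. The SAP takes this interval out of the treatment-emergent window and specifies no count table for it. The exclusion also depends on something that happens later, namely whether the subject goes on to wear a second dispensed lens. If followed as written, a non-serious event after first dispensed-lens exposure could be missing from the tabulated rates in refit subjects while the same event is counted in subjects who exit. At stake is the completeness of the descriptive AE tables, not an inference.

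**Working it through.** **1. Classes side by side.**

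| Onset of event | Protocol (synopsis Safety, 11.7) | SAP 5.3.1 |
|---|---|---|
| After consent, before first dispensed lens | Pre-treatment, listed | Pre-treatment, listed |
| During Dispense 1 wear | Treatment-emergent | Treatment-emergent, counted and listed |
| After last Dispense 1 wear, subject exits | No rule stated | Treatment-emergent, counted and listed |
| After last Dispense 1 wear, before Dispense 2 wear | No rule stated; no third class named | Between-treatment, listing specified, no count table |
| After last Dispense 2 wear, before exit | No rule stated | Treatment-emergent, counted and listed |

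**2. One event, two outcomes.** Take two subjects with the same exposure history. Each takes off the last Dispense 1 lens, and a non-serious ocular event starts before the follow-up visit. Subject A is judged well fitted and exits: the event is in the count table. Subject B is refit and later wears Dispense 2: the event is in a listing only. Nothing about the exposure before onset differs between them. A rule that excluded off-lens time would exclude both events. A rule that counted from first exposure to exit would include both.

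**3. Is Dispense 2 a different treatment?** Protocol section 9 assigns the lens brand once per subject and the fitting guide once per site. Protocol 10.2.1 has the refit done under the site's assigned guide, with a new prescription. So the brand and guide stay the same, and the event in step 2 does not fall between two different assigned products.

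**4. Consistency within the SAP.** SAP 5.3.3 gives device deficiencies two classes, pre-treatment and treatment-emergent, with no between-treatment class. SAP 5.3.2 counts grade increases of 2 or more from baseline to any later visit, unscheduled ones included, without excluding the interval. A finding at an unscheduled visit in the gap could therefore enter the biomicroscopy count while the matching adverse event stays out of the AE count.

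**5. Can the interval be longer than zero?** By default it is nil. Protocol 10.2.1 lets the Follow-up 1 visit serve as Dispense 2, and 10.2.2.2 waives the repeat slit-lamp exam when refit lenses are dispensed then. The stated maxima fit a zero gap:
- participation: 7 (Visit 1 to Dispense 1) + 13 + 13 = 33 days, as in Protocol 10.1;
- wear: 13 + 13 = 26 days, as in Protocol 9.2.

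A gap can still occur. SAP 5.3.2 treats same-day redispensing as a condition. Protocol 10.3 allows a refit to start from an unscheduled visit to which the subject may come with lenses already out. With 10-day wear periods and a 7-day wait for Dispense 1, 33 − (7 + 10 + 10) = 6 days would remain within the participation limit.

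**6. Size.** The documents give no refit rate, event rate or gap length, so the number of events affected cannot be computed. For scale only, assuming tables by lens brand at the planned 60 or so subjects per lens (120 eyes), one ocular event in one eye is 1/120 = 0.8 percentage points and one nonocular event is 1/60 = 1.7 points. These show what a single event is worth; they do not estimate how many there will be.

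**The case against.** The best defence is that the protocol leaves room for an exposure split. Its synopsis ties the treatment-emergent class to treatment-specific exposure, and under Treatments it gives the duration of treatment per dispensed lens, so Dispense 1 and Dispense 2 can be read as separate periods. Nowhere does the visible protocol say when the treatment-emergent period ends or how off-lens time is handled. Protocol 11.2.1 itself puts safety analyses on a treatment-emergent basis, so limiting the tables to that class follows it. On this view the SAP only fills in a boundary that the protocol left open. That much stands, and a reader who infers that the SAP contradicts the protocol outright goes further than the documents allow.

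A reader might also infer that these events disappear from the report. The SAP does not say so. It promises to account for all events and to list between-treatment events. It also speaks of separate analysis and presentation for them, which may leave room for a table although none is specified. The serious AE summary is not expressly limited to treatment-emergent events. Finally, Protocol section 11 allows departures from the analysis plan to be described in the clinical study report, which is not available here, so a failure to document cannot be alleged.

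It is also fair that the interval is nominally nil, and that the tail between last wear and exit should usually be short too. What the defence does not explain is why off-lens time before exit stays treatment-emergent while off-lens time before a refit does not.

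**Conclusion.** The point holds as a minor one. SAP 5.3.1 introduces a class that the visible protocol does not name, and its boundary makes counting depend on whether a refit follows. This is an unreconciled and internally inconsistent rule. Compared with counting all events from first dispensed-lens exposure to exit, it can only lower the tabulated rates, and only through subjects who are refit. The effect is probably small, given the default of redispensing at the follow-up visit, and cannot be quantified from the documents. No study conclusion changes: safety is descriptive with no hypothesis tests, all events are listed, events with onset during Dispense 1 wear are counted, and serious events in the gap may still be summarised.

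This rests on two assumptions: that redacted text holds no further AE class or table, and that the listing is the only output intended for between-treatment events. Confidence is moderate rather than high, because the protocol's exposure wording gives the SAP some footing.

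**What to change.** Preferred: keep the class, but in SAP 5.3.1 add a count and percentage table for it by System Organ Class and Preferred Term, with eyes as the unit for ocular events, subjects for nonocular events, and relationship to lens shown. A single table of all events after first dispensed-lens exposure would do as well. State that the serious AE summary includes between-treatment events. Record the departure from the protocol's two classes by either route in Protocol section 11, an amendment or the clinical study report. The cost is one small extra table and a few sentences.

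Alternative: delete the between-treatment exclusion, count events from first dispensed-lens exposure to exit under the lens actually worn, and flag gap events in the listing. This simplifies the derivation and brings the SAP back to the protocol's two classes. The cost is that reported rates may be slightly higher and may include a few off-lens events. The flag lets a reader separate them.
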